11.2. Sample Size Determination

The enrollment projections of the contributing Phase 1, 2 and 3 clinical studies are estimated to result in enrollment of up to approximately 3,000 subjects.

The proposed study is based on analysis of prospective cohort data provided by investigators on subjects exposed to Ad26.ZEBOV and/or MVA-BN-Filo (or placebo). The study may include bias related to the observational nature of the data and potential lack of data due to loss to follow-up or essential data not collected routinely. Loss to follow-up may be pronounced in countries where infrastructure for data collection is lacking. Additionally, the study's ability to detect serious adverse events and the precision of these rates are based on the number of subjects participating in the study and completing study follow-up; however, this number is unknown.

11.3. Analysis Sets

The Full Analysis set includes all subjects who were enrolled in this study and have at least one post-baseline visit, regardless of the occurrence of protocol violations.

The Restricted Analysis set includes all subjects who were enrolled in this study and have at least one post-baseline visit, have no major protocol deviations deemed to affect safety endpoints and have not been enrolled in any other clinical study.

The study endpoints will be analyzed based on the Full Analysis set as the primary analysis population. Additionally, the study endpoints may be analyzed based on the Restricted Analysis set as a secondary analysis population (sensitivity analysis).

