2. COHORT 2: PREGNANCY OUTCOMES

Data collection schedule for female subjects who became pregnant with estimated conception within 28 days after vaccination with MVA-BN-Filo (or placebo) or within 3 months after vaccination with Ad26.ZEBOV (or placebo) in a Phase 1, 2, or 3 clinical study:

	Visit 1 ^a	End of Pregnancy Follow-up ^a	
	Baseline (Start of Data Collection) ^b	End of Pregnancy	
Subject information			
Subject consent ^c	X		
Selection criteria	X		
Demographics ^d	X		
Ongoing subject review			
Serious adverse events ^{d,e}	X	X	
Medication and vaccinations ^{d,f}	X	X	
Pregnancy follow-upg	X	X	
Study completion/withdrawal			
Transition to Cohort 1h		X¹	

- a. Only the first visit is a study site visit; data collection at the end of the pregnancy will preferably occur through a phone call. If not possible by phone, a study site visit needs to be organized.
- b. Data collection can start when a signed ICF is available for the current study. Preferably, this occurs at the last visit of the subject's original study. If this is not possible, baseline data will be collected when a signed ICF is available and data will be captured retrospectively from the subject's last visit in the original study up to the moment of enrollment in the current study.
- c. Before the start of data collection in this study, all subjects and/or their legally-acceptable representative (where applicable) must sign an ICF for the current study indicating that he or she understands the purpose of and procedures required for the study and is willing to participate in the study.
- d. Relevant data will be copied from the analysis data set of the subject's original study. Any relevant new information should be added in the CRF of the current study.
- e. All serious adverse events in subjects exposed to Ad26.ZEBOV (or placebo) and/or MVA-BN-Filo (or placebo) are to be documented. Data collection should start with study enrollment and continue until the end of the pregnancy.
- f. Any medication taken within a period of 30 days prior to the onset of a serious adverse event and up to the resolution of the serious adverse event.
- g. Information on obstetric history, maternal/paternal risk factors, pregnancy outcome (including spontaneous/elective abortion, intrauterine death/stillbirth, information on delivery).
- h. After the pregnancy, female subjects will continue to be followed up in Cohort 1. A live-born child will be followed up in Cohort 3.

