3. COHORT 3: OFFSPRING

Data collection schedule for children born to female subjects who became pregnant with estimated conception within 28 days after vaccination with MVA-BN-Filo (or placebo) or within 3 months after vaccination with Ad26.ZEBOV (or placebo) in a Phase 1, 2, or 3 clinical study:

	Visit 1 ^a	Visit 2 ^a	Subsequent Visits ^a	End of Study ^a
	Baseline (Start of Data Collection) ^b	Month 6	Every 6 Months	60 Months After Birth
Subject information				
Subject consent ^c	X			
Selection criteria	X			
Demographics	X			
Medical history ^d	X			
Ongoing subject review				
Serious adverse events ^e	X	X	X	X
Medication and vaccinations ^f	X	X	X	X
Growth measurements ^g	X	X	X	X
Study completion/withdrawal				
End-of-study form				X ^h

- a. Preferably, offspring from vaccinated female subjects will visit the study site for every study visit. If not possible, the child may be visited at home by study site staff or a qualified health care worker for data collection.
- b. Data collection can start when a signed ICF is available for the current study (at birth or as soon as possible after birth). If this is not possible, baseline data will be collected when a signed ICF is available and data will be captured retrospectively from birth up to the moment of enrollment in the current study.
- c. Before the start of data collection in this study, the subject's parent or legally-acceptable representative (where applicable) must sign an ICF for the current study indicating that he or she understands the purpose of and procedures required for the study and is willing to let their child participate in the study.
- d. Medical history of the child may include information on birth (preterm/full term), presence of birth defects, medical interventions beyond routine interventions at birth and relevant information from the mother's pregnancy follow-up, family history of growth (details on stature of parents and siblings).
- e. All serious adverse events are to be documented. Data collection should start with the time of birth and continue for 60 months.
- f. Any medication taken within a period of 30 days prior to the onset of a serious adverse event and up to the resolution of the serious adverse event.
- g. Height, weight, growth percentiles.

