- h. When an enrolled subject completes or withdraws from the study, or is lost to follow-up, the investigator will complete the end-of-study form for the individual subject and provide a specific date for the end-of-study observation(s).

ABBREVIATIONS

Ad26 adenovirus serotype 26

Ad26.ZEBOV Ad26 vector expressing the glycoprotein of the Ebola virus Mayinga variant

AIDS acquired immunodeficiency syndrome

BN Bavarian Nordic CRF Case Report Form EBOV Ebola virus

eDC Electronic Data Collection

EU European Union GCP Good Clinical Practice

GP glycoprotein

HIV human immunodeficiency virus ICF Informed Consent Form IEC Independent Ethics Committee

IM intramuscular(ly)

IRB Institutional Review Board

MARV Marburg virus

MVA Modified Vaccinia Ankara

MVA-BN-Filo Modified Vaccinia Ankara Bavarian Nordic vector expressing multiple filovirus proteins

NHP non-human primates NP nucleoprotein

PCR polymerase chain reaction

RNA ribonucleic acid SUDV Sudan virus

SUSAR Suspected Unexpected Serious Adverse Reaction

TAFV Tai Forest Virus

TCID₅₀ tissue culture infective dose

US United States

VISP vaccine induced seropositivity

vp viral particles

WHO World Health Organization

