Participating sites will enter data into the CRF into an electronic data collection (eDC) system. The CRF will direct the site regarding which data are required for collection. Participating sites will be trained on the use of the eDC system. Data collected should be recorded accurately, correctly and promptly for each subject during the study. Further details of CRF completion procedures are presented in Section 17.5.

The sponsor will perform on-site monitoring visits as frequently as necessary. The monitor will record dates of the visits in a site visit log that will be kept at the participating site. Further details of monitoring procedures are presented in Section 17.8.

When an enrolled subject completes or withdraws from the study, the investigator will complete an end-of-study form for the individual subject and provide a specific date for the end-of-study observation(s). When a subject withdraws before completing the study, the reason for withdrawal is to be documented in the CRF and in the source documents (see Section 10 for details).

After unblinding of their original study, subjects who received placebo will be withdrawn from further participation. This also applies to pregnant subjects who received placebo (ie, subjects enrolled in Cohort 2) or offspring from vaccinated female subjects who received placebo (ie, subjects enrolled in Cohort 3).

Subjects who appear to be lost to follow-up will be contacted, per local practice, and the data recorded in the CRF. Subjects unable to be reached within 365 days of their last follow-up will be considered "lost to follow-up" unless subsequent contact is established. Subjects lost to follow-up will have all data included for analysis unless the subject had specified upfront that their data is to be excluded from analysis.

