11.1. Endpoints

The following endpoints will be analyzed:

- Incidence of serious adverse events in subjects exposed to Ad26.ZEBOV and/or MVA-BN-Filo in a Phase 1, 2 or 3 clinical study, up to 60 months after prime vaccination.
- Incidence of pregnancy with estimated conception within 28 days after vaccination with MVA-BN-Filo or within 3 months after vaccination with Ad26.ZEBOV.
- Incidence of pregnancy by pregnancy outcome.
- Incidence of live-born children from a pregnancy with estimated conception within 28 days after vaccination with MVA-BN-Filo or within 3 months after vaccination with Ad26.ZEBOV.
- Incidence of serious adverse events in children born from a pregnancy with estimated conception within 28 days after vaccination with MVA-BN-Filo or within 3 months after vaccination with Ad26.ZEBOV up to 60 months after birth.

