11.5. Safety Analyses

The verbatim terms used in the CRF by investigators to document serious adverse events will be coded using the Medical Dictionary for Regulatory Activities (MedDRA). All serious adverse events will be included in the analysis. For each serious adverse event, the percentage of subjects who experience at least 1 occurrence of the given event and the number of events per person-year (where applicable) with corresponding 2-sided 95% confidence intervals will be provided, for each cohort and by original randomization (active vaccine versus placebo). In addition, these analyses will be provided by age group for Cohort 1.

The incidence of pregnancy, incidence of pregnancy outcomes (including spontaneous/elective abortion, intrauterine death/stillbirth, information on delivery) and incidence of live-born children will be summarized by original randomization (active vaccine versus placebo). Only pregnancies with estimated conception within 28 days after vaccination with MVA-BN-Filo or within 3 months after vaccination with Ad26.ZEBOV, and live-born children from these pregnancies, will be included.

Results for subjects who received active vaccine or placebo will be presented separately.

A summary for subjects who die or who discontinue due to a serious adverse event will be provided.

The use of medications taken in relation to serious adverse events will be summarized.

Additional summaries, listings, datasets, or subject narratives may be provided, as appropriate.

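### The primary analysis set requires a post-baseline visit, so enrolled subjects who die or are lost before the first follow-up point can leave the SAE incidence analysis together with their events

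*Protocol*

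**What the plan says.** Section 11.3 defines the Full Analysis set as one that "includes all subjects who were enrolled in this study and have at least one post-baseline visit, regardless of the occurrence of protocol violations", and then states: "The study endpoints will be analyzed based on the Full Analysis set as the primary analysis population". The Restricted Analysis set, offered as an optional sensitivity analysis, carries the same post-baseline condition. No other set is defined.

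The SAE endpoint in Section 11.1 covers subjects exposed in an earlier "clinical study, up to 60 months after prime vaccination". The offspring endpoint runs to 60 months after birth.

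The Time and Events Schedule puts the first post-baseline point at Month 6 in Cohorts 1 and 3. In Cohort 2 it is the end of pregnancy, where "data collection at the end of the pregnancy will preferably occur through a phone call". In Cohort 1, too, only the first visit is a site visit and later contacts are preferably by phone.

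SAE information can already be on file at baseline. For Cohorts 1 and 2 it is copied from the original study and updated retrospectively. For Cohort 3, when consent comes after birth, "data will be captured retrospectively from birth up to the moment of enrollment in the current study".

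Section 11.5 says: "All serious adverse events will be included in the analysis". Section 9.1 says: "Subjects lost to follow-up will have all data included for analysis", unless the subject asked in advance for exclusion.

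**The concern.** Membership of the primary set depends partly on the outcome being measured. Section 12.3.1 treats the cause of any death as an SAE. A subject who dies between enrolment and the first follow-up point has had that event, yet may have only a baseline visit and so fall outside the set. Survivors keep their first six months of person-time while those who died in that period are removed, so fatal SAE incidence is biased downward. The sharpest case is an infant enrolled at birth who dies before Month 6.

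SAEs recorded at baseline also go, for anyone who dies or is lost before the first contact, although the endpoint clocks start at prime vaccination or birth. In Cohort 2, women lost before the end of pregnancy can drop out of the incidence-of-pregnancy endpoint.

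The study tests no hypothesis. Its product is a set of descriptive incidence rates, so a distortion in who is counted goes straight into the result.

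**Working it through.** **Consistency check.** The sections can be set side by side for an enrolled subject with no post-baseline visit.

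| Source | Treatment of this subject |
|---|---|
| Section 11.3, Full Analysis set | Excluded |
| Section 11.3, Restricted set | Excluded |
| Section 11.5 | All SAEs analysed |
| Section 9.1 | If lost, all data analysed unless the subject opted out |
| Section 11.5, summary of deaths | Population not named |

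Sections 9.1 and 11.5 do not refer to the post-baseline condition, and Section 11.3 makes no exception for them. The statements cannot all be followed.

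**Size.** The protocol states no mortality, SAE or early-loss rate, so it has no figure to reproduce. The only input from the document is enrolment of up to about 3,000 (Section 11.2). All rates below are assumptions, and the calculations take the narrow reading under which every early death is excluded.

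*Share of on-study deaths before Month 6.* With constant hazard λ per year and T months of follow-up remaining:

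share = (1 − exp(−0.5λ)) / (1 − exp(−λT/12))

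For λ from 0.002 to 0.01:

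- T = 54: 11.2–11.3%
- T = 48: 12.5–12.7%
- T = 36: 16.7–16.9%
- T = 60 (Cohort 3 from birth): 10.1–10.2%

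*Cohort 1, N = 3,000, λ = 0.005, T = 48.*

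- Deaths: 3,000 × (1 − exp(−0.02)) = 59.4, or 1.98%.
- Deaths before Month 6: 3,000 × (1 − exp(−0.0025)) = 7.5.
- Full Analysis set: (59.4 − 7.5) / (3,000 − 7.5) = 1.73%.

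With mortality of 1, 3 or 10 per 1,000 person-years, the expected deaths in the first six months are 1.5, 4.5 or 15.

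*Cohort 3, 5 deaths per 100 infants.* The retained risk is (5 − e) / (100 − e), where e is the number of deaths before Month 6.

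- 10% early (constant hazard), e = 0.5: 4.5%
- 25% early (assumed), e = 1.25: 3.8%
- 50% early (assumed), e = 2.5: 2.6%

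A small-cohort example with Clopper-Pearson 95% intervals: 3/60 is 5.0% (1.0–13.9). It becomes 2/59 = 3.4% (0.4–11.7) if one death is early, or 1/58 = 1.7% (0.04–9.2) if two are.

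*All SAEs, with subjects excluded for any reason.* If 1%, 5% or 10% of 3,000 have no post-baseline visit, 30, 150 or 300 are excluded. Take an SAE risk of 2% in those retained.

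- Risk three times higher in the excluded: 1.8, 9 or 18 subjects with an SAE are removed. The Full Analysis set shows 2.0% against 2.04%, 2.2% or 2.4% in all enrolled.
- Equal risk: the percentage is unbiased, but 0.6, 3 or 6 subjects with an SAE are still removed.

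**The case against.** The strongest reply is that *visit* is undefined and cannot mean a site visit in Cohort 1, where follow-up is by phone. A Month 6 call that learns of a death from relatives, an unscheduled SAE report, or the dated end-of-study observation required for every withdrawal might all count. Few early deaths would then be lost. Sections 9.1 and 11.5 also show that the sponsor means to report everything, and deaths get their own summary. This stands in part: a broad reading would shrink the exclusion, perhaps nearly to nothing. But the protocol does not state that reading, and the primary set should not turn on it. The summary of deaths names no population and is not said to correct the incidence rates.

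Other limits also stand:

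- The warning about loss in Section 11.2 concerns follow-up in general, so it says nothing about how many are lost before the first contact.
- A subject who misses Month 6 but is reached later satisfies the condition.
- For subjects merely lost, the direction of bias is unknown.
- In Cohort 2, any ascertained outcome itself creates the post-baseline point, so mainly the count of pregnancies is exposed.
- Using 3,000 for Cohort 1 is generous, because it is the upper projection for the whole study and includes placebo recipients who leave after unblinding.

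Reporting of SAEs within 24 hours protects detection of individual cases but does not repair the rates.

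**Conclusion.** The concern holds and should be fixed. As written, Section 11.3 permits an outcome-dependent exclusion from the primary SAE incidence analysis, its sensitivity set cannot reveal it, and it contradicts Sections 9.1 and 11.5. The contradiction needs no assumption. The downward direction is clear for fatal SAEs under the narrow reading, but not for SAEs in subjects merely lost. The size cannot be derived from the protocol. Under the assumed rates it is about a quarter of a percentage point in fatal SAE risk in Cohort 1 (1.98% to 1.73%). In Cohort 3 it ranges from half a point (5.0% to 4.5%) to about half of the risk (5.0% to 2.6%) if deaths cluster early. The Cohort 3 figures concern only infants enrolled before death.

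**What to change.** Define the Full Analysis set in Section 11.3 as all enrolled subjects with a signed consent form, without a post-baseline condition. Count SAEs on each endpoint's own clock: from prime vaccination in Cohort 1, during pregnancy in Cohort 2 and from birth in Cohort 3. Include those copied or captured retrospectively at baseline. End person-time at death, withdrawal or last contact. Align Sections 9.1 and 11.5, and name the population for the summary of deaths. A set requiring at least one post-baseline visit or contact, with that term defined, can stay as a sensitivity analysis.

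The cost is one sentence in Section 11.3 plus the alignment, with no extra data. The drawback is that an unknown number of subjects with little or no follow-up in this study enter the denominator, although those in Cohort 1 still bring person-time from the original study. Children who die before consent remain unenrolled under either definition, so the change does not recover them.

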5.1. Inclusion Criteria

Each potential subject must satisfy all of the following criteria to be enrolled in the current study:

- 1. Criteria modified per amendment 1
- 1.1 Criterion modified per amendment 2
- 1.2 Male or female who participated in a Phase 1, 2 or 3 clinical study with Ad26.ZEBOV and/or MVA-BN-Filo and has been exposed to Ad26.ZEBOV and/or MVA-BN-Filo (or placebo) (Cohort 1);

or

Female who participated in a Phase 1, 2 or 3 clinical study with Ad26.ZEBOV and/or MVA-BN-Filo and became pregnant with estimated conception within 28 days after vaccination with MVA-BN-Filo (or placebo) or within 3 months after vaccination with Ad26.ZEBOV (or placebo) (Cohort 2);

or

Child born to a female subject exposed to Ad26.ZEBOV and/or MVA-BN-Filo (or placebo) in a Phase 1, 2, or 3 clinical study who became pregnant with estimated conception within 28 days after vaccination with MVA-BN-Filo (or placebo) or within 3 months after vaccination with Ad26.ZEBOV (or placebo) (Cohort 3).

Note: Each local authority will determine which cohorts will be opened for enrollment in their region. It is not mandatory to open all cohorts for enrollment. As a result, a local authority may restrict enrollment to 1 or 2 cohorts, rather than allowing enrollment in all cohorts.

2. Must sign an ICF for the current study (or their legally acceptable representative must sign) indicating that he or she understands the purpose of, and procedures required for, the study and is willing to participate in the study (or let their child participate).

Note: Assent is also required of children capable of understanding the nature of the study (typically 7 years of age and older) as described in Section 16.2.3.

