10.2. Withdrawal From the Study

A subject may be withdrawn from data collection in this study for any of the following reasons:

- Withdrawal of consent
- Lost to follow-up
- Death

After unblinding of their original study, subjects who received placebo will be withdrawn from further participation. This also applies to pregnant subjects who received placebo (ie, subjects enrolled in Cohort 2) or offspring from vaccinated female subjects who received placebo (ie, subjects enrolled in Cohort 3).

Subjects who are subsequently enrolled as a subject in another non-sponsor clinical study do not need to be withdrawn from the study. It is accepted that data collection in this study may be restricted by confidentiality agreement terms and/or conditions of another concurrent clinical study.

When a subject withdraws before completing the study, the reason for withdrawal is to be documented in the CRF and in the source documents.

If a subject is lost to follow-up, every reasonable effort must be made by the study-site personnel to contact the subject and determine the reason for withdrawal. The measures taken to follow up must be documented. In the event that the status of the subject cannot be determined and the

subject is considered to be lost to follow-up, an end-of-study form for the individual subject will be completed and a specific date for the last observation will be provided.

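### The Restricted Analysis set excludes whole subjects for joining any other clinical study: read literally this removes Cohorts 1 and 2, and read as probably meant it selects on an event during follow-up and overstates fatal SAE rates

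*Protocol*

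**What the plan says.** Protocol Section 11.3 defines two sets. The Full Analysis set takes enrolled subjects with at least one post-baseline visit, whatever their protocol violations. The Restricted Analysis set adds two conditions, that subjects "have no major protocol deviations deemed to affect safety endpoints and have not been enrolled in any other clinical study". The second has no exception for the original study, no time window and no censoring rule.

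The roles are clear: "The study endpoints will be analyzed based on the Full Analysis set as the primary analysis population". The Restricted set may additionally be used, as a secondary sensitivity population.

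Section 5.1 sets entry. Cohort 1 takes a "Male or female who participated in a Phase 1, 2 or 3 clinical study with Ad26.ZEBOV and/or MVA-BN-Filo" who was exposed to vaccine or placebo. Cohort 2 takes a "Female who participated in a Phase 1, 2 or 3 clinical study with Ad26.ZEBOV and/or MVA-BN-Filo and became pregnant" within the stated windows. Cohort 3 takes a "Child born to a female subject exposed to Ad26.ZEBOV and/or MVA-BN-Filo (or placebo) in a Phase 1, 2, or 3 clinical study", so the child itself need not have been in an earlier study.

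On later studies, Section 10.2 says: "Subjects who are subsequently enrolled as a subject in another non-sponsor clinical study do not need to be withdrawn from the study". The one consequence it names is that "data collection in this study may be restricted by confidentiality agreement terms and/or conditions of another concurrent clinical study".

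Section 11.5 reports the percentage of subjects with at least one occurrence of each SAE and the number of events per person-year, with 95% confidence intervals. It also summarises deaths.

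**The concern.** There are two problems, depending on how the condition is read.

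As written, it contradicts the entry criteria. Every Cohort 1 and Cohort 2 subject has been enrolled in another clinical study, because that is how they became eligible. A programmer following the text would find nobody from either cohort.

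Read as Section 10.2 suggests, the condition concerns a study joined later or concurrently. Membership of the set is then known only at the end of follow-up. A subject who joins another study in year 4 loses all earlier person-time and SAEs too, although these were collected before the other study could have had any influence. Selecting on a future event can distort a rate by itself, so a difference between the Full and Restricted results could arise from the selection and be taken for something else. This is the only sensitivity population that Section 11.3 names.

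**Working it through.** The protocol states no figure that depends on this definition. The approximately 3,000 subjects in Section 11.2 are an enrollment projection, so there is nothing to reproduce.

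**Step 1: literal reading.** Setting Section 11.3 beside Section 5.1 leaves 0 subjects from Cohorts 1 and 2. Only Cohort 3 children can qualify.

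**Step 2: fatal SAEs, joining unrelated to health.** Assumptions, none of them from the protocol: follow-up in this study T = 4 years; constant death rate λ of 0.002 or 0.005 per person-year; constant joining rate μ = −ln(1 − p)/T, where p is the proportion joining; a = λ + μ.

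A subject who dies at time t stays in the set with probability exp(−μt), and a survivor with the smaller probability exp(−μT). Per subject enrolled, the Restricted set therefore contains:

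- deaths: D = (λ/a)(1 − e^(−aT))
- person-time: Y = λ[(1 − e^(−aT))/a² − T·e^(−aT)/a] + T·e^(−aT)

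Example with p = 20% and λ = 0.002: μ = 0.0558, a = 0.0578, e^(−aT) = 0.7936, D = 0.00714, Y = 3.188. D/Y = 0.00224 against a true 0.00200, a ratio of 1.12.

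| Join another study | Restricted rate / true rate (λ = 0.002; 0.005) |
|---|---|
| 5% | 1.026; 1.026 |
| 10% | 1.055; 1.054 |
| 20% | 1.120; 1.120 |
| 30% | 1.201; 1.201 |

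For small λ the ratio tends to p / [(1 − p)(−ln(1 − p))], which gives 1.026, 1.055, 1.120 and 1.202. The result therefore hardly depends on λ or T once p is fixed.

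With censoring at joining, deaths are (λ/a)(1 − e^(−aT)) and person-time is (1 − e^(−aT))/a. Their quotient is exactly λ.

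**Step 3: first non-fatal SAE.** This was simulated with 2,000,000 subjects, T = 4 years and λ = 0.02 per person-year (assumed). The joining rate is μ before the first SAE and μ × HR after it. Entries are the estimated rate divided by the true rate.

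| Joining (nominal) | HR 1/3: exclude; censor | HR 1: exclude; censor | HR 3: exclude; censor |
|---|---|---|---|
| 5% | 1.021; 1.004 | 0.999; 0.999 | 0.953; 1.001 |
| 10% | 1.036; 1.001 | 0.997; 0.998 | 0.901; 0.998 |
| 20% | 1.076; 0.998 | 0.999; 1.000 | 0.810; 1.002 |

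At HR 1 the retained subjects are a random subset, so there is no bias. If joining becomes less likely after an SAE, exclusion overstates the rate; if more likely, it understates it. Censoring returns the true rate within simulation error.

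**Step 4: joining driven by underlying health.** Assume 80% healthy subjects (0.01 SAE per person-year) and 20% frail (0.05), with joining rates of 0.10 and 0.02 per year over 4 years. The true rate is 0.8 × 0.01 + 0.2 × 0.05 = 0.0180.

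- Exclusion: weights 0.8·e^(−0.4) = 0.536 and 0.2·e^(−0.08) = 0.185, so 72% of subjects are kept. Rate = (0.00536 + 0.00923)/0.721 = 0.0202, or +12%.
- Censoring: mean times 3.297 and 3.844 years, so person-time is 2.637 + 0.769 = 3.406 of 4 years (85%). Rate = (0.02637 + 0.03844)/3.406 = 0.0190, or +6%.

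With equal joining rates in the two groups, both biases vanish. Here censoring roughly halves the bias but does not remove it.

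**The case against.** The case for leaving the definition alone has several parts.

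- **Vocabulary.** The protocol regularly calls the parent trial the subject's original study and uses another study for a later one. An analyst would hardly build an empty Cohort 1, and the SAP, not shown here, may clarify. This makes the intended meaning likely, but Section 11.3 still does not state it. It also leaves open whether studies joined before baseline, other sponsor studies and non-interventional studies count.
- **Data quality.** Section 10.2 mentions only confidentiality limits on data collection, so the set may be meant to keep subjects with uncompromised SAE capture. That is a fair purpose, but it concerns time after joining and does not justify deleting the time before.
- **Weight.** The set is optional and secondary, the Full Analysis set has no such exclusion, and no test or sample size depends on it. All of this stands and limits the importance of the point.
- **Cost.** The data items listed in the Time and Events Schedule and Section 9.1 include no date of joining another study. This stands.

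A reader might go further and infer that fit subjects are preferentially removed, so that all SAE rates are overstated. The documents never link joining another study to health, and Step 3 shows that the direction can reverse. A reader might also take the analysis as meant to isolate the effect of other studies' products; Section 11.3 states no such purpose. Nor does the literal reading empty the whole set, since Cohort 3 children remain.

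**Conclusion.** The point holds as a defect of definition in a secondary population. Literally, the Restricted set has no Cohort 1 or Cohort 2 subjects. Under the likely intended reading, it conditions on an event during follow-up and discards valid earlier person-time and events.

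The bias that needs no health link is the one for fatal SAEs: about +2.6% to +20% as the proportion joining goes from 5% to 30%. That rests on constant rates, an assumed 4 years and assumed joining proportions, because the protocol gives none. For non-fatal SAEs, neither the existence nor the direction of a bias can be settled from the protocol. The calculation there covers first events, whereas Section 11.5 counts events per person-year.

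It would be wrong to conclude that the main safety results are affected. They rest on the Full Analysis set.

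**What to change.** In Section 11.3, make two changes:

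1. State that the original vaccine study does not count as another clinical study.
2. For the events-per-person-year sensitivity analysis, keep Full Analysis set subjects without major deviations affecting safety endpoints. Censor their person-time and events at the date of enrollment in another interventional study, instead of excluding them.

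Confine the censored analysis to the rate. The percentage of subjects with an event does not allow for unequal follow-up.

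The cost is a sentence or two, minor programming, and the enrollment date for the other study, which may need one added CRF field. A little person-time after joining is lost from this analysis. If joining depends on underlying health, censoring reduces the bias but does not remove it (Step 4), and the report should say so.
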